### 7.2 Analysis of anti-SARS-CoV-2 titers

Analysis of titers will also primarily be descriptive, at days 0,4, 7 and 14 post study treatment administration.

### 7.3 Endpoints

#### **Primary Endpoint:**

Cohort 1: Delta SOFA Score (change in SOFA score) from baseline at the time of plasma infusion to 96 hours post infusion (ICU cohort).

The Sequential Organ Failure Assessment (**SOFA**) **Score** is a mortality prediction **score** that is based on the degree of dysfunction of six organ systems. The **score** is calculated on admission and every 24 hours until discharge using the worst parameters measured during the prior 24 hours. Calculation of SOFA score is described in Appendix 1.

Cohort 2: Combined primary end point of death, intubation or ICU transfer (non-ICU cohort).

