### **4.2 Study Definitions:**

1. Enrolled: From time consented to participate until designated as a screen failure or have either been discontinued from the study or completed it.
2. Screen Failures: signed informed consent, but then determined to be ineligible or withdraws before being treated.
3. Discontinued: enrolled, but then withdrawn by investigator or subject withdraws consent
4. Completed: Subjects are considered to have completed when they are followed through day 60 or day of death if death occurred prior to day 60

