### **5. Study population**

Patients will be enrolled in 2 cohorts independent of each other. Cohort 1 will consist of patients who are admitted to the ICU. Cohort 2 will consist of patients who are admitted to a non-ICU floor. Patients transferring from non-ICU to ICU floors or vice versa will be

analyzed in the cohort corresponding to the location of signing consent. Each cohort will be analyzed independently.

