## **Primary Hypotheses:**

Cohort 1: the probability of decrease in SOFA score of at least 2 after 96 hours from the intervention is higher than 20%. An increase to 40% would be clinically meaningful.

Cohort 2: the probability of death, intubation or ICU transfer is lower than 60%. A decrease to 45% would be clinically meaningful.

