## **7.4 Analysis of primary endpoints**

The proportion of patients achieving the primary endpoint will be reported with a two-sided 95% exact Clopper-Pearson confidence interval. The primary hypothesis will be evaluated using an exact binomial test at a one-sided 2.5% significance level.

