### 7.5.5 Ventilator-free days

Ventilator-free days will be considered only in Cohort 1. It will be defined as the number of days during 28 days after the intervention that the subject is alive and does not require ventilator support. Ventilator-free days will be summarized with median and inter-quartile range.

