## 7.6 Sample size considerations

The cohort sizes were selected to achieve at least 80% power of rejecting the null hypotheses at a one-sided 2.5% significance level if the true probability of the primary outcome is at its clinically meaningful value. A single stage exact binomial study design was used.

Cohort 1: With 41 subjects the study will have 80% power to reject the null hypothesis of  $\leq 20\%$  probability of a 2-point decrease in SOFA at a one-sided 2.5% significance level, if the underlying probability is 40%. The treatment will be considered successful if 14 or more subjects achieve the primary endpoint.

Cohort 2: With 90 subjects the study will have 80% power to reject the null hypothesis of  $\geq 60\%$  probability of death, intubation or ICU transfer, if the underlying probability is 45%. The treatment will be considered successful if 44 or fewer subjects achieve the primary endpoint.

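### Cohort 2's composite primary endpoint and its 60% and 45% rates have no stated start or end day, and assigning the cohort at consent leaves ICU transfers and intubations before plasma in the analysis

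*Combined protocol and SAP*

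**What the plan says.** Section 7.3 gives the Cohort 2 endpoint as "Cohort 2: Combined primary end point of death, intubation or ICU transfer (non-ICU cohort". The protocol summary and Section 4.1 list the same three components, again without a start or an end. The hypothesis in Section 7.3 reads "Cohort 2: the probability of death, intubation or ICU transfer is lower than 60" per cent, with 45% as the clinically meaningful value; no period is attached to either rate. Section 7.4 states that "The primary hypothesis will be evaluated using an exact binomial test at a one-sided 2.5% significance level", and Section 7.6 sets the rule for 90 subjects: "The treatment will be considered successful if 44 or fewer subjects achieve the primary endpoint".

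Other endpoints in the plan do have windows. Cohort 1 is measured "from baseline at the time of plasma infusion to 96 hours post infusion (ICU cohort". Section 7.5.5 counts ventilator-free days over the "number of days during 28 days after the intervention". Section 7.5.2 estimates mortality at 60 days after the intervention. Section 4.2 treats subjects as complete once "followed through day 60 or day of death", and Section 11.3 puts study completion at 60 days from infusion.

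On cohort membership, Section 5 says that patients who move between floor and ICU are "analyzed in the cohort corresponding to the location of signing consent". Table 1 and Section 8 place consent and screening on days -3 to 0, and Section 6.2 has plasma follow consent and baseline procedures. Section 5.1 does not make eligibility depend on location and excludes mechanical ventilation only beyond 14 days.

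**The concern.** Two gaps meet in one endpoint.

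The first is the window. Cohort 2 is a single-arm comparison with a fixed 60%, so there is no concurrent control whose rate would move with the length of observation. The cut-off of 44 has its stated error rates only if events are counted over the same period that the 60% describes. If the periods differ, the error can go either way: false success if the counting window is shorter, or a missed effect if it is longer.

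The second is the start. A patient who consents on the floor, is moved to the ICU or intubated before plasma, and is then treated belongs to Cohort 2 under Section 5. Counting that event charges plasma with something that happened before it was given. Not counting it keeps in the denominator a patient who can no longer have one of the three component events. The plan does not say which applies, and neither gives a sound count. The replacement rule in Section 5.3 does not help, because it covers only subjects who were never treated.

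**Working it through.** **Inputs.** n = 90, success if at most 44 events, null 60%, target 45% (Sections 7.3 and 7.6); exact binomial test at one-sided 2.5% (Section 7.4). The documents give neither the timing of events nor the frequency of transfers before infusion, so every other rate or count below is an assumption.

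**Step 1: the plan's own figures.** With X the number of events:
- P(X ≤ 44 | n = 90, p = 0.60) = 0.0213
- P(X ≤ 44 | n = 90, p = 0.45) = 0.8019
- P(X ≤ 45 | n = 90, p = 0.60) = 0.0347, above 0.025

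So 44 is the correct cut-off and the stated 80% power reproduces. The design arithmetic is sound.

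**Step 2: window mismatch.** Keep the 44-event rule and let the no-effect rate over the window actually used be p. False success is P(X ≤ 44 | 90, p):

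| Assumed no-effect rate | False success |
|---|---|
| 60% (as designed) | 2.1% |
| 58% | 5.1% |
| 57% | 7.4% |
| 55% | 14.5% |

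In the other direction, if a longer window raises the no-effect rate to 65%, false success is P(X ≤ 44 | 90, 0.65) = 0.1%. Power for the same 15-point fall is then P(X ≤ 44 | 90, 0.50) = 45.8%.

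**Step 3: events before infusion, counted.** If k patients enter with the endpoint already met, success needs at most 44 - k events among the other 90 - k. The probability is P(Bin(90 - k, p) ≤ 44 - k):

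| k | Power (others at 45%) | Type I error (others at 60%) |
|---|---|---|
| 1 | 76.9% | 1.7% |
| 3 | 69.5% | 1.0% |
| 5 | 60.9% | 0.6% |

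This reading costs power and does not inflate type I error.

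**Step 4: events before infusion, not counted.** The direction reverses. At the extreme where none of the k patients has any later component event, type I error is P(Bin(90 - k, 0.60) ≤ 44): 2.8%, 4.7% or 7.6% for k = 1, 3 or 5. These are upper limits, since such patients can still die and some can still be intubated.

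**Step 5: analysing only patients on the floor and not intubated at infusion.** Take the largest cut-off with P(X ≤ c | n, 0.60) ≤ 0.025:

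| n | Cut-off | Type I error | Power at 45% |
|---|---|---|---|
| 90 (places refilled) | 44 | 2.1% | 80.2% |
| 89 | 43 | 1.7% | 76.9% |
| 87 | 42 | 1.8% | 76.5% |
| 85 | 41 | 1.9% | 76.1% |

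Without refilling, one excluded patient leaves power where counting that patient would have left it (76.9%). With three or five, power is 76.5% against 69.5%, or 76.1% against 60.9%.

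**The case against.** The strongest reply is that day 60 is implied. Sections 4.2 and 11.3 end follow-up there, Section 7.5.2 uses it for mortality in both cohorts, and a proportion with no earlier limit most naturally counts events through completed follow-up. This largely stands. A reader might infer that day 28, day 60 and the hospital stay are equally open; the text does not support that, because the two shorter horizons add a limit that it does not contain. Section 7.5.5 is weak support for day 28: it restricts ventilator-free days to Cohort 1, although the endpoint lists assign them to the non-ICU cohort. What remains is that day 60 is not attached to the composite, nothing says that 60% and 45% are day-60 rates, and time zero is absent.

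A second reply is that the horizon rates are assumed. That is correct. Nothing in the documents shows that plausible windows differ by 5 points, so 14.5% is not a forecast. At 58%, only 2 points below the null, false success is still 5.1%.

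A third reply is that Section 5 is only an allocation rule and does not say that events before infusion count. That is true, but no text excludes them, and either handling is unsatisfactory.

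A reader might also infer that the Day 28 contact in Section 8 would miss an ICU admission or intubation after discharge. The documents do not support that: the contact includes evaluation of new medical conditions and adverse events, Section 11.2.3 records onset times, and Section 11.3 documents events to day 60.

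**Conclusion.** The point holds. The Cohort 2 composite and both of its benchmark rates lack a time zero and an end day. The rule fixing the cohort at consent, followed as written, keeps patients whose ICU transfer or intubation preceded plasma.

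The size depends on facts that the documents do not give. With an assumed 1, 3 or 5 such patients counted as events, power is 76.9%, 69.5% or 60.9% rather than 80.2%. With an assumed no-effect rate of 58%, 57% or 55% over the window used, false success is 5.1%, 7.4% or 14.5% rather than 2.1%.

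A reader might infer that the sample size or the cut-off is miscalculated, or that the trial is bound to declare success falsely. Neither follows: 44 of 90 is right for a 60% null, and counting events before infusion lowers type I error. The defect is in the definition, and it matters because the only comparator is a fixed rate.

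**What to change.** 1. Define the Cohort 2 endpoint as the first death, intubation or ICU transfer after the start of infusion and through one fixed day. Day 60 has the best support in the existing text.
2. State that 60% and 45% refer to that window, in patients who are on the floor and event-free at infusion, and give the basis for 60%. If the benchmark changes, recompute the cut-off and check the sample size.
3. For the Cohort 2 primary analysis, include patients who are on the floor and not intubated at the start of infusion. Report the others separately rather than moving them into Cohort 1, so that its 41 patients and 20% null are unaffected.
4. State that the exact test in Section 7.4 applies to the number analysed and that 44 holds for n = 90. Without refilling, the rule becomes 43 of 89, 42 of 87 or 41 of 85.

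A best-case and worst-case sensitivity analysis for patients with unknown outcome is a reasonable option but is not needed to resolve this point.

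The cost is mainly wording and a justification of the benchmark. Infusion start time is already recorded on Day 0 and follow-up already runs to day 60. If 60% is confirmed and 90 patients qualify at infusion, 44 of 90 stands unchanged. If transfers before infusion occur, the price is either a few extra patients, which may take enrolment above 131, or power of about 76 to 77%. Cohort counts would also have to be tracked at infusion.

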## **Primary Hypotheses:**

Cohort 1: the probability of decrease in SOFA score of at least 2 after 96 hours from the intervention is higher than 20%. An increase to 40% would be clinically meaningful.

Cohort 2: the probability of death, intubation or ICU transfer is lower than 60%. A decrease to 45% would be clinically meaningful.

## **7.4 Analysis of primary endpoints**

The proportion of patients achieving the primary endpoint will be reported with a two-sided 95% exact Clopper-Pearson confidence interval. The primary hypothesis will be evaluated using an exact binomial test at a one-sided 2.5% significance level.

## **7.5 Analysis of secondary endpoints**

### **7.5.1 Type and duration of respiratory support**

The number of patients requiring each type of respiratory support will be tabulated. The duration of support will be summarized with median and inter-quartile range. For the purposes of this protocol respiratory support will be captured and classified in the following categories:

1. Supplemental Oxygen by nasal cannula, simple mask, non-rebreather mask and defined by flow rate in liters/min
2. High Flow Nasal Oxygen with flow rates and FiO2 setting
3. Non-invasive positive pressure ventilation with flow, FiO2 and pressure settings defined
4. Mechanical Ventilation with FiO2, Pressure and ventilator settings defined
5. Extra corporeal Membrane Oxygenation (ECMO).

### **7.5.2 Overall mortality within first 60 days**

The overall survival of the subjects will be estimated using the Kaplan-Meier method and presented with 95% confidence bands. Subjects may be censored if they had a routine discharge (not hospice, or another hospital), and could not be contacted for further follow-up. Overall mortality at 60 days post-intervention will be estimated using the Kaplan-Meier estimate.

### **7.5.3 Hospital LOS and in-hospital mortality**

In-hospital mortality will be estimated as the observed proportion of subjects who died during the hospital stay and presented with a 95% exact Pearson confidence interval. Hospital length of stay will be considered only among subjects discharged alive and will be summarized with median and inter-quartile range.

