##### **Secondary endpoints:**

1. Type and duration of respiratory support (see definitions in Section 7.5.1)
2. Overall Mortality within first 60 days
3. Hospital LOS and in hospital mortality
4. ICU LOS and ICU mortality
5. Ventilator-free days (non-ICU cohort)
6. Incidence of secondary infections / co infections

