### **7.5.4 ICU LOS and ICU mortality**

ICU length of stay and mortality will be considered in Cohort 1 and among subjects in Cohort 2 who are admitted to an ICU. ICU mortality will be estimated as the observed proportion of subjects who died during the hospital stay and presented with a 95% exact Clopper-Pearson confidence interval. ICU length of stay will be considered only among subjects discharged alive and will be summarized with median and inter-quartile range.

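### Length of stay is summarised only in patients discharged alive, so anyone still in hospital or ICU at Day 60 drops out of it without counting as a death

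*Combined protocol and SAP*

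**What the plan says.** Hospital stay and ICU stay are listed secondary endpoints, each paired with a mortality measure (Sections 4.1 and 7.5). Neither has a test, threshold or comparator.

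- Hospital stay (Section 7.5.3): "Hospital length of stay will be considered only among subjects discharged alive and will be summarized with median and inter-quartile range".
- ICU stay (Section 7.5.4), for Cohort 1 and for Cohort 2 patients who enter an ICU: "ICU length of stay will be considered only among subjects discharged alive and will be summarized with median and inter-quartile range". The text does not say whether the discharge meant is from the ICU or from hospital.
- Deaths (Section 7.5.3): "In-hospital mortality will be estimated as the observed proportion of subjects who died during the hospital stay". Section 7.5.4 words ICU mortality the same way: "ICU mortality will be estimated as the observed proportion of subjects who died during the hospital stay". Both carry exact 95% confidence intervals. Section 7.5.2 adds a 60-day figure: "Overall mortality at 60 days post-intervention will be estimated using the Kaplan-Meier estimate".
- End of follow-up (Section 4.2): "Subjects are considered to have completed when they are followed through day 60 or day of death if death occurred prior to day 60".

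No section says how a patient still in hospital or ICU at Day 60 enters length of stay. No censoring or competing-event rule is given for it.

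**The concern.** The set of patients summarised is defined by what happens after treatment. Leaving out deaths is a common convention, and this plan reports them alongside. Patients still in hospital at Day 60 are different. In Section 7.5.3 they count as non-deaths in the mortality proportion and are absent from length of stay, so neither summary shows their long stay. Section 8 records location at Day 28, but Section 7 plans no analysis of it.

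These are by definition the longest stays. Dropping them cuts the upper tail and shortens the median and upper quartile even as a description of survivors.

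There is also a question of reading. A median among patients discharged alive does not say how long it takes the treated cohort to leave hospital alive. A reader who takes it alone as a sign of benefit would be misled.

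**Working it through.** The documents give no expected stay, death rate or share still in hospital at Day 60, so there is no plan figure to reproduce. The check has four steps.

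**1. Where each patient goes under the stated rules (hospital stay)**

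| Status at Day 60 | In length of stay? | Counted as a death? |
|---|---|---|
| Discharged alive | Yes | No |
| Died in hospital | No | Yes |
| Still in hospital | No | No |

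The third row appears in neither summary. For ICU stay the row depends on what discharge means: a patient who leaves the ICU alive and then dies on the ward could be in or out.

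**2. Size of the Day 60 loss alone (all inputs assumed)**

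Assume survivor stay, counted from infusion, is log-normal with median m and log-SD s = 0.8. Φ is the standard normal distribution function.

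- Share of survivors discharged by Day 60: F = Φ(ln(60/m)/s).
- Median among those discharged by Day 60: m × exp(s × Φ⁻¹(F/2)).

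For m = 20: ln(3)/0.8 = 1.373, so F = 0.915 and F/2 = 0.458. Then Φ⁻¹(0.458) = −0.107, and 20 × exp(0.8 × −0.107) = 18.4 days.

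| Survivor median m | Still in at Day 60 (1 − F) | Planned median | Upper quartile, all survivors | Upper quartile, planned |
|---|---|---|---|---|
| 12.0 | 2.2% | 11.7 | 20.6 | 19.8 |
| 20.0 | 8.5% | 18.4 | 34.3 | 29.5 |
| 25.0 | 13.7% | 21.8 | 42.9 | 33.8 |

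The upper quartiles are m × exp(s × Φ⁻¹(0.75)) for all survivors and m × exp(s × Φ⁻¹(0.75F)) under the plan. With s = 1.0 the losses are larger: medians of 12.0, 20.0 and 30.0 become 11.2, 16.9 and 22.0.

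**3. A different quantity: time to live discharge in all treated patients**

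If a fraction d die in hospital, half the cohort has left alive when the survivor distribution reaches 0.5/(1 − d). For m = 12 and s = 0.8:

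| d | 0.5/(1 − d) | Half the cohort out alive | Planned median |
|---|---|---|---|
| 0% | 0.500 | 12.0 | 11.7 |
| 20% | 0.625 | 15.5 | 11.7 |
| 40% | 0.833 | 26.0 | 11.7 |

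Stay is taken as unrelated to death here, so the planned median does not move with the death rate.

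**4. Another different quantity: days spent in hospital by all patients**

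In a simulation of 1,000,000 patients (m = 12, s = 0.8, 40% deaths, death times log-normal with log-SD 0.8, stays capped at 60 days), the planned median was 11.7 to 11.8 days. The all-patient median was 8.5 days when deaths came early (median day 5) and 16.0 days when they came late (median day 25). Dropping deaths can therefore move this quantity either way.

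**The case against.** The plan states its population openly, so the median is a fair description of survivors who were discharged. Deaths are not lost: they appear in the same sections with exact intervals, and again as 60-day mortality. The endpoint is descriptive, in two single-arm cohorts. The success rules (14 or more of 41 in Cohort 1; 44 or fewer of 90 in Cohort 2) use other outcomes. With short stays, plausible for the 90 non-ICU patients, the Day 60 loss is about 0.3 days. All of this stands and keeps the point small.

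The Day 60 exclusion is also inferred. Section 4.2 ends a subject's follow-up at Day 60, but Section 7.5.3 sets no such limit on stay. Section 15.1 makes medical records the primary source, so a later discharge date could be abstracted. That stands too, which is why the point is conditional.

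A reader might infer three stronger things, which the documents do not support:

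- *That the plan understates time to recovery.* No such endpoint exists; the one listed is "Hospital LOS and in hospital mortality". For days in hospital, dropping deaths can push the figure either way (step 4).
- *That more deaths would produce a shorter reported stay.* That needs the extra deaths to fall on patients who would otherwise have stayed long. When stay is unrelated to death, the planned median is merely insensitive to mortality (step 3).
- *That the whole gap in step 3 (11.7 against 26.0 days at 40% deaths) is error in the plan.* Nearly all of it comes from asking a different question, with deaths counted as never discharged. Only 0.3 days of it is the Day 60 loss.

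**Conclusion.** The point holds in a limited form. On the plain wording, patients still in hospital or ICU at Day 60 are neither in length of stay nor among the deaths. If no later discharge date is used, the reported median and upper quartile are too short even for survivors. Under assumed log-normal stays with log-SD 0.8, the median loses 0.3 days at a survivor median of 12, about 1.6 days at 20 and about 3.2 days at 25. The documents cannot show which case applies.

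Separately, the survivor median is not a measure of time to live discharge in all treated patients and should not be read alone as benefit. It remains a legitimate description if labelled as such.

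This is a minor, optional improvement. It touches a descriptive secondary endpoint and neither primary decision rule.

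**What to change.** For each cohort:

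- Add the cumulative incidence of live discharge to Day 60, from hospital and, where applicable, from the ICU. Treat death as a competing event and censor patients still in at Day 60 there.
- Report the proportion out alive at Days 14, 28 and 60, and the median time to live discharge if it is reached.
- Keep the survivor median and inter-quartile range, labelled as conditional on live discharge. Give the denominator and the numbers excluded, split into died and still in at Day 60.
- State in Section 7.5.4 whether discharge means from the ICU or from hospital.
- State the time origin of each stay, which Sections 7.5.3 and 7.5.4 leave open.

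Follow-up to Day 60 is already planned, and discharge and death dates are needed for the existing summaries, so no new visits are required. The cost is one more descriptive summary per setting and cohort.
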